### **8.5 Adverse Events of Special Concern**

Adverse events of special concern for this study are categorized into the following groups: 1) suicidal ideation, etc.; 2) spontaneous abortion/miscarriage; 3) neuropsychiatric events including a subset of psychosis/mania-related events; 4) cardiac arrhythmias; 5) combined insomnia; 6) weight decreased; 7) decreased appetite. Appendix 14.7 lists the PTs and corresponding MedDRA codes that fall under each category. AEs of special concern will be summarized by category of interest, SOC, PT and treatment group.

A listing of AEs of special concern, stratified by weight, will be presented.

### **8.6 Clinical Laboratory Evaluations**

The following laboratory tests will be performed at Screening (Visit 1) and EOS (Visit 6):

- Clinical Chemistry: Alanine aminotransferase (ALT), Alkaline Phosphatase (ALP), Aspartate aminotransferase (AST), Bicarbonate (HCO3), Bilirubin (Total, Direct, Indirect), Blood Urea Nitrogen (BUN), Calcium (Ca), Chloride (Cl), Creatinine, Glucose, Magnesium (Mg), Phosphorus (P), Potassium (K), Protein (Total), Sodium (Na), Uric Acid, Albumin
- Hematology: Hemoglobin, Hematocrit, Platelet Count, RBC Count, WBC - Total Count, WBC Differential, (Basophils, Eosinophils, Lymphocytes, Monocytes, Neutrophils)
- Urinalysis: Blood, Glucose, Ketones, Leukocyte esterase, Microscopic examination, Nitrites, pH, Protein

Summary statistics for these laboratory panels (clinical chemistry, hematology and urinalysis) will be provided by treatment group and visit. Laboratory data will also be summarized in shift tables presenting summary statistics of raw data and change from baseline values (means, standard deviations, medians, ranges). All clinical laboratory assessments will be listed for each panel.

In addition, the incidence of markedly abnormal post-baseline laboratory values (MAPLV) will be presented to examine the frequency and percentage of subjects that have values that are potentially clinically significant (PCS). These abnormal values will also be flagged in the laboratory listings. These criteria are outlined in Appendix 14.4.

## **8.7 Physical and Neurological Examinations**

A full physical examination will be performed at Screening (Visit 1) and at the EOS (Visit 6). Body weight will also be measured at Screening (Visit 1), Visit 4, Visit 5, and at the EOS (Visit 6). Height will be measured at Screening (Visit 1).

Clinically significant physical examination findings, as judged by the investigator, at screening will be recorded as medical history and after screening will be recorded as AEs or pre-treatment events depending on the timing in relationship to the first dose of study drug. Abnormal physical exam results will appear in medical history and/or AEs displays and will not be displayed separately.

Neurological examinations will be performed at Screening (Visit 1) and at the EOS (Visit 6) and the parameters will be assessed by the investigator as normal or abnormal. Neurological examination assessments will be summarized using summary statistics for categorical variables (normal/abnormal) by visit. A shift table for baseline condition versus the worst result during the course of the study period (normal/abnormal) will be presented by treatment.

## **8.8 Vital Signs**

Vital signs, including respiratory rate; body temperature; supine, standing, and orthostatic blood pressure; supine, standing, and orthostatic heart rate; BMI; and body weight, will be measured at all scheduled in-person study visits (Screening [Visit 1 and Visit 2], Visit 4, Visit 5, and EOS [Visit 6]).

Supine systolic blood pressure, standing systolic blood pressure, orthostatic systolic blood pressure, supine diastolic blood pressure, standing diastolic blood pressure, orthostatic diastolic blood pressure, supine heart rate, standing heart rate, orthostatic heart rate, respiratory rate, body temperature, body weight, and BMI will be summarized descriptively for each visit by treatment group for the absolute value and change from baseline values using descriptive statistics.

In addition, the incidence of sponsor-defined markedly abnormal post-baseline vital sign values will be presented to examine the frequency and percentage of subjects that meet the PCS criteria outlined in Appendix 14.5. Vital signs will also be presented in a listing by subject and visit. The listing will include a flag for abnormal values.

## **8.9 Electrocardiography (ECG)**

A 12-lead ECG will be recorded at Screening (Visit 1) and the EOS visit (Visit 6). All ECGs will be obtained in the supine position, after the subject has been resting supine for at least 5 minutes. The ECG parameters collected will include heart rate, PR interval, RR interval, QT interval, QTc with Bazett correction (QTcB) and QTc with Fridericia correction (QTcF) intervals, QRS duration, and interpretation, including any noted abnormalities. The ECGs will be reviewed and interpreted by the investigator. All data will be assessed for clinical significance.

ECG measurements, overall interpretation and clinical significance will be summarized descriptively for baseline, each post-dose evaluation, and change from baseline to each post-dose evaluation by treatment group. QT interval, QTcB, and QTcF will also be summarized by < 460 msec, >= 460 msec, < 500 msec, and >= 500 msec, as well as change from baseline < 30 msec, >= 30 msec, < 60 msec, and >= 60 msec, by visit, treatment and age group (6-9 years, 10-13 years (age range up to 13 to account for any subjects who were 12 years at screening but 13 years at time of ECG measurement)).

In addition, the incidence of sponsor-defined markedly abnormal post-baseline ECG values will be presented to examine the frequency and percentage of subjects that meet the PCS criteria outlined in Appendix 14.6. ECG results will also be presented in a listing by subject and visit. The listing will include a flag for abnormal values.

Shifts from baseline to EOS visit ECG results will be presented by treatment group for the overall interpretation (e.g., normal to abnormal, or abnormal to normal).

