Abbreviations: ADHD-RS-IV HV = ADHD Rating Scale Version IV Home Version (modified for investigator administration), β -hCG = beta-human chorionic gonadotropin, K-SADS-PL = Schedule for Affective Disorders and Schizophrenia for School-Age Children- Present and Lifetime version, PERMP = Permanent Product Measure of Performance, SKAMP = Swanson, Kotkin, Agler, M-Flynn, and Pelham Scale, TSH = thyroid stimulating hormone

^a Seven (± 2) days after the last dose of study drug, all subjects will return to the clinic and complete assessments.

^b Heart rate and blood pressure will be measured at approximately the same time on Day 1 and Day 15.

^c Including practice SKAMP assessments, practice PERMP tests, and other planned activities intended to familiarize subjects with the classroom setting.

^d Classroom sessions will be started at approximately 8 AM, 10 AM, 12 PM, 2 PM, 4 PM, 6 PM, and 8 PM.

^e Any positive urine β -hCG test should be confirmed by serum β -hCG.

^f Pre-treatment events will be collected from the time of informed consent until the first study drug administration.

^g The ADHD-RS-IV HV may be completed in person or by telephone contact on Day -9, -8, or -7.

Table 3: Sample Laboratory Classroom Day Schedule (Day 15)

Nominal Time	Actual Time	Arrival	PERMP/SKAMP	Meal/snack	Dismissal
	6:30 am	X			
	7:30 am			X	
12 h post-dose	8:00 am		X		
	9:45 am			X	
14 h post-dose	10:00 am		X		
16 h post-dose	12:00 pm		X		
	12:30 pm			X	
18 h post-dose	2:00 pm		X		
	2:30 pm			X	
20 h post-dose	4:00 pm		X		
22 h post-dose	6:00 pm		X		
	6:30 pm			X	
24 h post-dose	8:00 pm		X		
	8:45 pm				X

Abbreviation: h = hour, PERMP = Permanent Product Measure of Performance, SKAMP = Swanson, Kotkin, Agler, M-Flynn, and Pelham Scale

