One study was completed that evaluated the safety, tolerability, pharmacokinetic, and pharmacodynamic properties of dasotraline in pediatric (6 – 12 years) and adolescent (13 - 17 years) subjects with ADHD. In this multicenter, open-label study 105 subjects were assigned to single oral doses of dasotraline 1 - 16 mg in a dose-escalating manner. Dasotraline was characterized by slow absorption (median t_{max} was 9.6 to 12 hours) and elimination (median $t_{1/2}$ was 56 to 84 hours) in both pediatric and adolescent subjects. The change in C_{max} with dose was slightly greater than dose proportional. Increase in overall exposure (AUC) with dose was greater than dose proportional. Apparent oral clearance was highest in the lowest dose group relative to the higher dose groups. No deaths, serious adverse events (SAE), or discontinuations because of an adverse event (AE) were reported in this study. The most frequently reported AE by investigators were tachycardia (25 subjects; 23.8%) and electrocardiogram QT prolonged (5 subjects; 4.8%), nearly all of which were considered related to study drug and mild in severity. Tachycardia AEs were reported in both age groups and in every dose cohort. Most events of tachycardia were reported on the day of study drug administration. No subjects experienced QT prolongations > 500 msec. Based on the centrally read electrocardiogram (ECGs) in the study, no clinically significant trends were identified within the ECG results. Blood pressure increased, blood pressure systolic increased, blood pressure orthostatic abnormal, and orthostatic hypotension AEs were reported in 1 subject each. Overall, after dosing, 90 subjects (85.7%) met predefined criteria for orthostatic tachycardia and 40 (38.1%) met predefined criteria for orthostatic hypotension.

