- Absolute values and changes from baseline in vital signs, body weights, and 12-lead ECGs
- Frequency and severity of suicidal ideation and suicidal behavior as assessed by the C-SSRS

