Double-blind Period: On Day 1 subjects will return to the clinic in the morning, and those meeting all inclusion and no exclusion criteria will be randomized (1:1) to receive 2 mg/day dasotraline, or placebo, and will attend classroom sessions in which they will be evaluated for ADHD symptoms using the SKAMP assessment. During this baseline classroom assessment (Day 1), subjects will be evaluated at regular intervals: approximately 8 AM, 10 AM, 12 PM, 2 PM, 4 PM, 6 PM, and 8 PM. Subjects will begin taking study drug on the evening of Day 1 (with or without food) after the final, 8:00 PM baseline classroom assessment. Subjects will take one dose each evening before bedtime for a total of 14 days. Study drug should be taken at approximately the same time each evening. The first dose of study drug may be administered in the clinic after all assessments are completed and before the subject leaves, or at home. On the night (Day 14) before the second classroom day, study drug must be taken at approximately 8 PM plus or minus 30 minutes. During the double-blind period, the clinical site will attempt to contact the subject's parent/legal guardian daily with a reminder to administer study drug. A dosing diary will be provided to the parent/legal guardian to record the date and time of each administration of study drug. On Day 15 subjects will return to the clinic in the morning at 6:30 AM and classroom sessions will be started at approximately 8 AM, 10 AM, 12 PM, 2 PM, 4 PM, 6 PM, and 8 PM to coincide with 12, 14, 16, 18, 20, 22, and 24 hours following the Day 14 dose.

End of Study: Seven (± 2) days after the last dose of study drug, all subjects will return to the clinic and complete assessments. After the EOS visit, all subjects will be referred for continuation of their care as determined by the investigator. Additionally, for subjects who complete the study or discontinue for tolerability or lack of efficacy reasons, the sponsor will provide support for approved ADHD medication costs for up to 3 months after participation in the study, if deemed medically appropriate by the subject's healthcare provider.

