11.5.2.2. Visit 5 (Day 15): Second Laboratory Classroom Day

At this visit the subject should arrive at the clinic by 6:30 AM and the following study-related procedures will be performed:

- Perform study drug accountability
- Collect dosing diary
- Record prior and concomitant medications
- Record AEs
- Measure weight, record BMI
- Collect vital signs once. For each subject the time should be the same as on Day 1.
- Administer C-SSRS since last visit version
- Collect samples for UDS, urine pregnancy test for females ≥ 8 years of age
- Conduct 7 classroom sessions according to the Laboratory Classroom Manual.

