11.5.3. Visit 6 (Day 21 \pm 2): End of Study

Final safety assessments will be completed at this visit. The following study-related procedures will be performed:

- Record prior and concomitant medications
- Perform physical and neurological examinations
- Measure weight, record BMI
- Collect vital signs
- Perform ECG
- Record AEs
- Administer C-SSRS since last visit version, ADHD-RS-IV HV
- Collect samples for clinical laboratories (hematology, serum chemistry, urinalysis), UDS, serum pregnancy test for females ≥ 8 years of age

All subjects including those who discontinue study drug prior to completion will be asked to return 7 (\pm 2) days after the last dose of study drug and complete the EOS visit.

After the EOS visit, all subjects will be referred for continuation of their care as determined by the investigator. Additionally, for subjects who complete the study or discontinue for tolerability or lack of efficacy reasons, the sponsor will provide support for approved ADHD medication costs for up to 3 months after participation in the study, if deemed medically appropriate by the subject's healthcare provider.

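### No 12-lead ECG is scheduled during treatment, so PR, QRS and QT/QTc are compared with placebo only 5 to 9 days after the last dose, at reduced exposure

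*SAP*

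**What the plan says.** The two documents agree on the ECG schedule. SAP 8.9 states: "A 12-lead ECG will be recorded at Screening (Visit 1) and the EOS visit (Visit 6". Protocol Table 2, the visit lists in Protocol 11.5 and SAP Appendix 14.1 show the same two time points. The Visit 5 (Day 15) list in Protocol 11.5.2.2 has no ECG; its cardiovascular entry is "Collect vital signs once. For each subject the time should be the same as on Day 1".

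On timing, Protocol 7.1 has "Subjects will take one dose each evening before bedtime for a total of 14 days", starting on the evening of Day 1. The final visit is set by "Seven (± 2) days after the last dose of study drug, all subjects will return to the clinic and complete assessments". Protocol 11.5.3 applies the same interval to children who stop early: "All subjects including those who discontinue study drug prior to completion will be asked to return 7" (± 2) days after the last dose.

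Protocol 6.2 lists as an endpoint "Absolute values and changes from baseline in vital signs, body weights, and 12-lead ECGs". Protocol 5.2 names the ECG in the safety objective, and Protocol 7.1 includes it among the measures that monitor safety throughout the study. SAP 8.9 plans summaries of change from baseline at every post-dose evaluation, QT/QTc categories (460 and 500 msec; changes of 30 and 60 msec), counts of markedly abnormal values and shift tables.

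**The concern.** All of these tables rest on one post-baseline recording, made after dosing has ended. PR, QRS, QT and QTc therefore have no scheduled comparison with placebo at on-treatment exposure. If a drug effect on these intervals falls as concentration falls, the difference between arms at Visit 6 will understate it.

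The gap reaches other parts of the plan. Protocol Appendix I asks the investigator to use ECGs in judging whether a child continues in the study, yet no ECG is scheduled between screening and the final visit. Clinically significant ECG findings become adverse events (Protocol 12.2). Prolonged QT, PR and QRS are among the events of special concern in SAP Appendix 14.7, which supply the outcome for the mg/kg ROC analysis in SAP 10. Systematic detection of those events is therefore post-treatment as well. SAP 9 plans no pharmacokinetic sampling, so exposure at Visit 6 cannot be measured or adjusted for.

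At stake is whether the report can say anything about ECG intervals on 2 mg/day in these children.

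**Working it through.** **Inputs**
- Last dose: evening of Day 14 (Protocol 7.1).
- Visit 6: 5 to 9 days after the last dose, i.e. 120 to 216 h, nominally 168 h (Protocol Table 2).
- Median half-life h: Protocol 4.3 reports that it "was 56 to 84 hours) in both pediatric and adolescent subjects". Median tmax in the same study: 9.6 to 12 h.

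**1. The plan's own date.** Day 14 + 7 = Day 21, window Day 19 to Day 23. This matches Table 2.

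**2. Level left at Visit 6, relative to the end of dosing.** Fraction = 2^(−t/h).

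| Time after last dose | h = 56 h | h = 84 h |
|---|---|---|
| Day +5 (120 h) | 2^(−120/56) = 22.6% | 2^(−120/84) = 37.1% |
| Day +7 (168 h) | 2^(−168/56) = 12.5% | 2^(−168/84) = 25.0% |
| Day +9 (216 h) | 2^(−216/56) = 6.9% | 2^(−216/84) = 16.8% |

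Day +7 is 168/56 = 3.0 or 168/84 = 2.0 half-lives.

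**3. Level left relative to Day 15, 12 h after the Day 14 dose.** This is the natural comparator, because it is when the first classroom session starts. Fraction = 2^(−(t−12)/h).
- Day +7: 2^(−156/56) = 14.5%; 2^(−156/84) = 27.6%.
- Over the window: lowest 2^(−204/56) = 8.0%; highest 2^(−108/84) = 41.0%.
- A one-compartment model with first-order absorption, 14 daily doses and tmax of 9.6 or 12 h gives 14.6% to 14.7% and 27.6% to 27.7% at day +7, so simple decay is adequate here.
- Against the 24-h level instead, day +7 gives 2^(−144/56) = 16.8% and 2^(−144/84) = 30.5%.

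**4. What Day 15 would offer.** Fraction of steady state after 14 doses (336 h) = 1 − 2^(−336/h): 98.4% for 56 h and 93.8% for 84 h. The 6:30 AM arrival is about 10.5 h after an 8 PM dose, inside the median tmax range. The sessions run from 12 to 24 h post-dose.

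**5. Effect on the SAP's own categories.** Assume that a QTc change is proportional to concentration, and ignore measurement noise. A child with a 60 msec rise at the Day 15 12-h level would show 60 × 0.145 = 8.7 to 60 × 0.276 = 16.6 msec at day +7. At the most favourable corner of the window (day +5, 84 h) the figure is 60 × 0.410 = 24.6 msec. A rise in the top change category on treatment would therefore be expected to fall below the 30 msec cut at Visit 6.

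**The case against.** **Heart rate.** Supine and standing pulse is measured on Day 15, summarised by visit and arm (SAP 8.8), and has markedly abnormal criteria (SAP Appendix 14.5). The earlier tachycardia findings, including "Most events of tachycardia were reported on the day of study drug administration", therefore concern a measure that does have an on-treatment comparison. This stands, and the point is confined to PR, QRS and QT/QTc.

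**Residual exposure.** A reader might infer that the ECG is taken off drug altogether. The documents do not support that: at these half-lives a meaningful fraction remains, and the SAP starts its adverse-event follow-up period only after the stop date plus 7 days. The accurate description is off treatment with declining exposure.

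**Prior evidence.** A reader might also infer that an ECG effect at 2 mg is already known. It is not. The study in Protocol 4.3 was open-label with single doses of 1 to 16 mg. QT-prolonged adverse events occurred in 5 of 105 subjects (4.8%), but no QT prolongation exceeded 500 msec and central reading found no clinically significant trends. It is a reason to measure and does not show an effect at 2 mg.

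**Early stoppers.** Moving every Visit 6 ECG to Day 15 would leave children who stop early, and are asked back only for Visit 6, with no scheduled post-baseline ECG. At the planned 12% dropout, that is up to 0.12 × 100 = 12 of 100 randomised. This stands and shapes the fix.

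**Crowding on Day 15.** The ECG needs at least 5 minutes of supine rest after the vital signs. For a cohort of 18 and one station (an assumption), 18 × 5 = 90 minutes, which fills the whole 6:30 to 8:00 arrival period. But the seven 30-minute sessions start two hours apart, so each of the six gaps is 90 minutes less any meal or other activity. The ECGs need not all precede the first session.

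Unscheduled visits and repeat ECGs are possible under the protocol, but they give no systematic comparison of the arms.

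**Conclusion.** The point holds for PR, QRS and QT/QTc. Their only scheduled comparison with placebo is made at roughly 15% to 28% of the Day 15 12-h exposure at day +7, and 8% to 41% across the visit window. A null result there would not support ECG safety on 2 mg/day.

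The schedule itself is certain, because both documents state it. The size rests on two assumptions: that the quoted half-lives apply at 2 mg/day, and that ECG effects follow concentration. On the first, Protocol 4.3 reports more than dose-proportional exposure and the highest clearance in the lowest dose group, so the residual at 2 mg could be lower than shown. On the second, if an effect outlasts the drug level, the dilution is smaller.

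The ECG analyses are descriptive and no ECG hypothesis is tested. The weakness is in what those tables can support; the primary efficacy result is untouched.

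**What to change.** For children who attend Visit 5, record the post-baseline ECG on Day 15, with the vital signs or between classroom sessions. Use it for the change-from-baseline, QTc-category, markedly abnormal and shift tables. The time of the Day 14 dose is already entered in the database (Protocol 9.5), so time since dose can be reported.

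Keep the Visit 6 ECG for children who stop early and have no Day 15 visit. Tabulate those recordings separately as post-treatment, with days since last dose.

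Update Protocol Table 2, 11.5.2.2 and 11.5.3, and SAP 8.9 and Appendix 14.1.

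The number of ECGs per child is unchanged, and the vendor's equipment is already supplied to sites (Protocol Appendix I). The costs are a somewhat fuller Day 15 and no post-treatment ECG for completers.

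The SAP lists three amendments (12.1) and describes site enrolment in the past tense (7.1.2), so Day 15 visits may already be complete. In that case the remedy is in reporting: label every ECG table as post-treatment, report days since last dose, reconcile the statements that ECG monitors safety throughout the study and is summarised at each post-dose evaluation with the two-ECG schedule, and draw no on-treatment ECG conclusion.

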## **8.10 Columbia Suicide Severity Rating Scale (C-SSRS)**

The C-SSRS is a brief investigator-administered questionnaire that provides for the identification, quantification, and standardized assessment of the occurrences and severity of suicidal ideation and behavior. Subjects will be assessed at Screening (Visit 1) using the Children's Baseline/Screening C-SSRS. For all subsequent testing (Visits 2, 4 and 5 and the EOS visit), the Children's Since Last Visit assessment will be utilized.

The frequency of suicidality using the C-SSRS will be summarized for each visit for each of the following outcomes:

- Number of subjects reporting at least one occurrence of suicidal ideation or

behavior.

- Number of subjects reporting any type of suicidal behavior.
- Number of subjects reporting any type of suicidal ideation.

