An analysis of covariance (ANCOVA) will be applied to evaluate the treatment effect for the primary efficacy endpoint between the dasotraline 2 mg/day and placebo groups for the intent-to-treat (ITT) population. The model will include treatment, mean SKAMP-Combined score at baseline, and site as fixed effects. The primary efficacy analysis will be repeated for the per protocol (PP) population. To explore the robustness of the primary efficacy analysis of change from baseline at Day 15 in ADHD symptoms in mean SKAMP-Combined score, 2 sensitivity analyses will be performed, a placebo-based multiple imputation pattern-mixture model (PMM) and a tipping point analysis using the PMM.

A similar ANCOVA model, as described above, will be used for the secondary efficacy endpoints for the ITT population.

Multiplicity Considerations: There will be no adjustment for multiplicity for the primary efficacy analysis, secondary efficacy analyses, or safety analyses.

Safety Analysis:

All safety analyses will be performed on the safety population. Overall AEs (or SAEs) and AEs (or SAEs) leading to discontinuation will be summarized by system organ class and preferred term by presenting the number and percentage of subjects with each AE. Descriptive statistics also will be provided by visit for observed values and changes from baseline for the following safety variables:

laboratory tests, vital signs, and ECG parameters. Frequency and severity of suicidality, as captured by the C-SSRS, will be summarized by visit.

Sample Size:

A post-hoc ANCOVA-LOCF analysis of data from the SEP360-305 laboratory classroom study was conducted to examine the effect of dasotraline 4 mg/day versus placebo in a subset of pediatric patients with ADHD aged 6-9 years old. This analysis showed an effect size in this subgroup of 0.95 (LS mean difference at Week 2 was 7.2 with a standard error of 2.2). Assuming a smaller effect size for dasotraline 2 mg/day vs. placebo than that of dasotraline 4 mg/day vs. placebo, an effect size of 0.7 was utilized for the sample size calculation.

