8. Subject has any diagnosis of bipolar I or II disorder, major depressive disorder, conduct disorder, obsessive-compulsive disorder, any history of psychosis, autism spectrum disorder, disruptive mood dysregulation disorder (DMDD), intellectual disability, Tourette's Syndrome, confirmed genetic disorder with cognitive and/or behavioral disturbances. Note: Subjects with oppositional defiant disorder (ODD) are permitted to enroll in the study as long as ODD is not the primary focus of treatment.
9. Subject has a first-degree relative (biological parent or sibling) with a history of schizophrenia, schizoaffective disorder, bipolar I disorder, or bipolar II disorder.
10. Subject has generalized anxiety disorder or panic disorder that has been the primary focus of treatment at any time during the 12 months prior to screening or that has required pharmacotherapy any time during the 6 months prior to screening.
11. Subject has evidence of any chronic disease of the central nervous system (CNS) such as tumors, inflammation, seizure disorder, vascular disorder, potential CNS related disorders that might occur in childhood (eg, Duchenne Muscular dystrophy, myasthenia gravis, or other neurologic or serious neuromuscular disorders).
12. Subjects with a history of persistent neurological symptoms attributable to serious head injury.
13. History of febrile seizure, drug-induced seizure, or alcohol withdrawal seizure is exclusionary.
14. Subjects taking anticonvulsants for seizure control currently or within the past 2 years are not eligible for study participation.
15. Subject has uncontrolled thyroid disorder as evidenced by thyroid stimulating hormone (TSH) ≤ 0.8 x the lower limit of normal (LLN) or ≥ 1.25 x the upper limit of normal (ULN) for the reference laboratory.
16. Subject answers "yes" to "Suicidal Ideation" item 4 (active suicidal ideation with some intent to act, without specific plan) or item 5 (active suicidal ideation with specific plan and intent) for any lifetime history on the C-SSRS Children's Lifetime/Recent assessment at screening.
17. Subject has any history of attempted suicide or clinically significant suicidal ideation, in the opinion of the investigator.
18. Subject has a history of severe allergies to more than 1 class of medication or multiple adverse drug reactions or has a history of allergic reaction or has a known or suspected sensitivity to any substance that is contained in the study drug formulations.

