15.3.6.7. Columbia-Suicide Severity Rating Scale (C-SSRS)

The number of subjects having any suicidal behavior or suicidal ideation from the C-SSRS evaluation will be summarized.

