### **12.2 Changes in the Analysis Planned in the Protocol**

No changes are planned as of the date of the SAP.

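### Severity of suicidal ideation and behavior is a stated secondary endpoint, but the planned C-SSRS tables count only any ideation, any behavior, or either, so escalation within ideation or between behavior types is not summarized by arm.

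*SAP*

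**What the plan says.** Protocol 6.2 lists as a secondary endpoint "Frequency and severity of suicidal ideation and suicidal behavior as assessed by the C-SSRS", and the synopsis lists the same endpoint. The synopsis paragraph on safety analysis adds: "Frequency and severity of suicidality, as captured by the C-SSRS, will be summarized by visit".

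The analysis sections are narrower. Protocol 15.3.6.7 says: "The number of subjects having any suicidal behavior or suicidal ideation from the C-SSRS evaluation will be summarized". SAP 8.10 first describes the C-SSRS as an instrument that assesses severity as well as occurrence. It then says: "The frequency of suicidality using the C-SSRS will be summarized for each visit for each of the following outcomes". The three outcomes are subjects with ideation or behavior, subjects with any behavior, and, for ideation, "Number of subjects reporting any type of suicidal ideation". Neither section mentions ideation item, most severe ideation, behavior type or shift from baseline.

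SAP 7.1.3 defines a baseline for the C-SSRS: the last value recorded before the first dose. SAP 8.10 plans nothing that uses it.

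**The concern.** Half of a two-part endpoint has no planned summary, and the protocol's synopsis and its statistics section disagree about whether there should be one. The protocol itself treats the level of ideation as important. Under Protocol 8.2, a lifetime yes to ideation item 4 or 5 excludes a child. Lower-level ideation does not exclude unless the investigator judges it clinically significant. A child may therefore enter with low-level ideation and escalate on treatment. In the planned C-SSRS tables that child would add one to the ideation count at both visits.

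Suicidality is also the first group of adverse events of special concern in SAP 8.5, and the C-SSRS is named in the safety objective in Protocol 5.2. With a planned 50 children per arm, one child is 1/50 = 2 percentage points. When counts are this small, the level reached is much of what separates a minor finding from a serious one.

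**Working it through.** The plan gives no figure on this point to reproduce. The check compares the endpoint text with the analysis text, then asks which changes the planned rows can show.

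**Step 1: the texts side by side.**

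| Place | Frequency | Severity | By visit |
|---|---|---|---|
| Synopsis and Protocol 6.2, endpoint | yes | yes | not stated |
| Synopsis, safety analysis | yes | yes | yes |
| Protocol 15.3.6.7 | yes | no | not stated |
| SAP 8.10 | yes, three yes/no rows | no | yes |

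**Step 2: which changes the rows can show.** Order a child's state as 0 = none, 1 to 5 = most severe ideation item, 6 = behavior (taken here to include ideation). With 7 states there are 7 × 6 / 2 = 21 possible upward moves:

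- From none to any other state: 6. At least one row changes.
- From ideation to behavior: 5. The behavior row changes.
- Within ideation, for example item 1 to item 4: 5 × 4 / 2 = 10. No row changes.

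So 6 + 5 = 11 moves register and 10 do not. These are counts of possible moves, not probabilities. Escalation from one behavior type to another falls outside this scale and is hidden for the same reason. The by-visit counts are also not linked within child, so splitting them by level would not by itself show who worsened.

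**Step 3: whether another table fills the gap.**

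- *General conventions.* SAP 3 summarizes all categorical assessments by arm and time point, but gives precedence to specific sections where they depart from it. SAP 8.10 names its own three outcomes.
- *Listings.* SAP 3 lists all data by subject, arm and time point. The item levels would be there, without a summary by arm.
- *Adverse events.* SAP 8.5 and Appendix 14.7 tabulate suicidality terms by arm, and SAP 8.4 tabulates events by maximum severity. Under Protocol 12.3 that severity is mild, moderate or severe, graded on discomfort and effect on daily activities. It is not the ideation item or behavior type. A C-SSRS answer enters these tables only if it is recorded as an adverse event.
- *Shift tables.* SAP 8.6, 8.7 and 8.9 plan them for laboratory values, neurological examination and ECG interpretation. SAP 8.10 plans none.

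**Step 4: the baseline for a shift.** The C-SSRS is scheduled at Visits 1, 2, 4, 5 and 6, with the since-last-visit version from Visit 2 on. Under SAP 7.1.3 the baseline is normally Visit 4, which looks back from Day 1 to Day -7, about 7 days. Visits 5 and 6 together cover Day 1 to Day 21 ± 2, or 18 to 22 days. Taking instead the worst of Visits 2 and 4 would conflict with SAP 7.1.3. It could also reach back to Day -35 in the protocol's schedule (Day -42 in the SAP's), longer than the post-dose period, and so could mask worsening.

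**The case against.** A reader might infer that any worsening on drug would be invisible. The documents do not support that: new ideation and a move from ideation to behavior change the planned rows.

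A reader might also infer that only the listings hold the information and that nothing compares the arms. That is too strong. Protocol 11.4.7 refers significant ideation findings to the investigator, and the adverse event definition in Protocol 12.1.1 includes worsening of existing conditions. Appendix 14.7 has separate terms for ideation, behavior, threat, attempt and completed suicide, and one for an abnormal C-SSRS. A child who reached item 4 on Day 15 might well appear in a by-arm table this way. What remains is that such an entry depends on a recorded event and carries no C-SSRS level.

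A third tempting reading is that the SAP misstates its relation to the protocol when it says "No changes are planned as of the date of the SAP". The statement is defensible, because SAP 8.10 follows Protocol 15.3.6.7 and adds detail to it. The conflict lies inside the protocol, between that section and the synopsis and endpoint list.

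Two further objections stand in part. Table specifications are in separate documents (SAP 1), so the tables may break the counts down further; the plan as written does not commit to it. And events are likely to be few. The example needs a child with ideation at baseline who passes the exclusion criteria, which are reviewed again on Day 1. A shift table may be mostly zeros, and a listing would show a single case directly. This limits the consequence but does not supply the promised summary.

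**Conclusion.** The point holds in a limited form. Followed as written, the plan yields no by-arm summary of C-SSRS severity, although severity is part of a stated secondary endpoint and the synopsis says it will be summarized by visit. What the C-SSRS tables miss is escalation within ideation (10 of the 21 upward moves on the scale above) and escalation between behavior types. Other worsening registers.

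The practical effect is probably small and does not touch the primary result. That judgment assumes few events among about 100 children screened for serious ideation; the documents give no rate against which to test it. The conclusion also assumes that the separate table specifications add nothing beyond SAP 8.10.

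**What to change.** In SAP 8.10, add the following:

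- By arm and visit, the number and percentage of subjects by most severe ideation item (none, 1 to 5) and by behavior type.
- By arm, a shift table from the baseline in SAP 7.1.3 (last pre-dose since-last-visit assessment, normally Visit 4) to the worst post-dose level at Visits 5 and 6. A footnote should say that the post-dose recall period is longer than the baseline one. The schedule is the same in both arms, so the comparison between arms is still fair.
- The lifetime screening result, shown separately because its recall period differs.

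Align Protocol 15.3.6.7 with the synopsis and endpoint list.

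The cost is SAP and protocol wording and one or two tables, mostly sparse, from data already collected. There is no added burden on children or sites.
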